## Investigational Plan Summary

Title:	XprESS Eustachian Tube Dilation Study
Study device:	XprESS™ Multi-Sinus Dilation System (XprESS device)
Study design:	A prospective, multicenter, 2-phase, controlled study. Phase 1 consists of a nonrandomized design. Phase 2 consists of a randomized design.
Enrollment:	A total of 50 subjects: Phase 1 – 10 nonrandomized balloon dilation subjects Phase 2 – 40 subjects randomized 1:1 to balloon dilation (treatment) or continued current medical therapy (control)
Treatment:	Phase 1: All subjects will receive balloon dilation Phase 2: Subjects will be randomized 1:1 to the following study arms: 

1. Control arm: Continued current medical management with ability to crossover to dilation after 6 weeks, if not improved

2. Treatment arm: Eustachian tube dilation – bilateral or unilateral, as indicated

Clinical centers:	Up to 7 US investigational centers
Inclusion criteria:	Subjects MUST : 

1. Be <math>\geq 18</math> years old

2. Have been diagnosed with Eustachian tube dysfunction (ETD) for no less than 12 months before enrollment with 3 or more of the following symptoms: ear pain, ear pressure, ringing in the ears, cracking or popping sounds in the ears, muffled hearing, or feeling that ears are clogged or “under water”

3. Have an overall ETDQ-7 score <math>\geq 3.0</math>

4. Have a record of failed medical management for ETD consisting of a minimum of either 4 weeks of daily intranasal steroid spray or 1 completed course of an oral steroid within the 12-month period before enrollment

5. Be a candidate for unilateral or bilateral transnasal balloon Eustachian tube dilation using the XprESS device

6. Have a temporal bone CT scan (showing the Eustachian tube) without contrast within 6 months of the enrollment date

7. Be able to read and understand English

8. Be able and willing to provide consent

9. Be willing to comply with the protocol requirements

Exclusion criteria:	Subjects MUST NOT : 

1. Have had any head or neck surgery (eg, adenoidectomy, tonsillectomy) including sinonasal surgery or ear tube placement performed within 3 months before enrollment

2. Require concomitant procedures at the time of study enrollment or procedure

3. Have ear tubes in place (tympanostomy tubes, myringotomy tubes, ventilation tubes, or pressure equalization tubes) or perforation of the tympanic membrane at the time of the study enrollment or procedure (patients with healed tympanic membranes after extrusion of tubes are not excluded)

4. Have patulous Eustachian tubes
5. Have had any previous laser tuboplasty surgery or microdebridement
6. Have temporomandibular joint (TMJ) disorders
7. Have early hydrops (Meniere's disease)
8. Have had head or neck radiation therapy or sinonasal malignancy
9. Have a diagnosis of chronic rhinosinusitis (CRS/RARS) that is uncontrolled
10. Have an immunodeficiency
11. Have craniofacial abnormalities or other anatomical conditions (eg, severely deviated septum, tumor, enlarged adenoids or tonsils, severe turbinate hypertrophy) that would prevent transnasal access of the Eustachian tubes
12. Have evidence of internal carotid artery dehiscence or anatomic abnormalities
13. Have uncontrolled allergies
14. Have unmanaged gastroesophageal reflux disease (GERD) or laryngopharyngeal reflux (LPR)
15. Be pregnant at the time of study enrollment or procedure
16. Be currently participating in any other drug or device clinical studies excluding postapproval or marketing registry studies

Objective:	To demonstrate the safety and efficacy of the XprESS device in treating patients with ETD.
Primary endpoints:	
 
• Comparison of mean change in overall ETDQ-7 scores from baseline to 6 weeks between randomization arms
 
• Complication rate
 

Secondary endpoints:	
 
• Mean change in overall ETDQ-7 score from baseline to follow-up (balloon dilation subjects)
 
• Technical success rate
 
• Revision dilation rate
 

Study assessments	
 
• Baseline
 
• 6-Week crossover evaluation (control subjects only)
 
• Procedure
 
• 6-Week postprocedure follow-up
 
• 3-Month postprocedure follow-up
 
• 6-Month postprocedure follow-up (for 510(k) submission and publication purposes)
 
• 12-Month postprocedure follow-up (for publication purposes)
 

Sponsor:	Entellus Medical Inc. United States
Data management and monitoring:	Entellus Medical Inc. United States

## Abbreviations and Acronyms

AE	Adverse event
ANSI	American National Standards Institute
CFR	Code of Federal Regulations (US)
CI	Confidence interval
CRF	Case report form
CRS/RARS	Chronic rhinosinusitis/recurrent acute rhinosinusitis
CT	Computed tomography
DICOM	Digital Imaging and Communications in Medicine
ENT	Ear, nose, and throat
EQ-5D	EuroQol-5 dimension survey
ET	Eustachian tube
ETD	Eustachian tube dysfunction
ETDQ-7	Eustachian tube dysfunction 7-item questionnaire
FDA	Food and Drug Administration (US)
GCP	Good clinical practices
GERD	Gastroesophageal reflux disease
HIPAA	Health Insurance Portability and Accountability Act of 1996 (US)
ICF	Informed consent form
IFU	Instructions for use
IRB	Institutional Review Board
LPR	Laryngopharyngeal reflux
PTA	Pure tone audiometry
SAE	Serious adverse event
UADE	Unanticipated adverse device effect
VAS	Visual analog scale

# 1 Background and Purpose

## 1.1 Background

The Eustachian tube (ET) connects the middle ear to the nasopharynx. It serves 3 functions: pressure regulation, deflection of pathogens/foreign objects, and middle ear fluid clearance. The ET is comprised of a bony isthmus and a cartilaginous region. The cartilaginous part of the ET is normally closed but opens when needed to equalize pressure within the middle ear. Transient opening of the ET occurs with yawning, swallowing, or popping of the ears.

Dysfunction of the Eustachian tube can result from the tube being too open (patulous ET), too closed (mechanical obstruction), or unable to efficiently open during swallowing (functional obstruction). Mechanical obstruction of the ET can be from either extrinsic (eg, tumors, adenoids, nasal septal deviations) or intrinsic (eg, inflammation, stenosis) mechanisms. Functional obstruction, a common cause of Eustachian tube dysfunction (ETD), occurs when the tube fails to open in the absence of a mechanical obstruction and can be caused by increased tubal compliance, inefficient opening mechanism, and/or abnormal pressures at either ET end.

When the ET does not function properly there is abnormal pressure equalization in the middle ear. Symptoms of ETD include fullness in the ear, dizziness, tinnitus, and pain or discomfort with barometric changes (eg, flying, diving). ETD can lead to tympanic membrane retraction, cholesteatoma, and hearing loss and is frequently associated with chronic otitis media. Chronic rhinosinusitis, allergic rhinitis, gastroesophageal reflux disease, and smoking exposure may all have roles in development of ETD.

Historically, treatments have been geared toward management or prevention of otitis media, not correcting the dysfunction of the ET. Recently, research has been initiated to study the possibility that balloon dilation could offer a minimally invasive treatment for ETD. It is thought that ET balloon dilation increases the luminal diameter, reduces local inflammation, and facilitates the muscular action necessary for ET opening. Theoretically, balloon dilation results in minimal mucosal injury, sparing the clearance and protective functions of the ET, while improving pressure equalization within the middle ear.

## 1.2 Purpose

The purpose of the current study is to collect 6-month safety and efficacy data on the use of the XprESS device to support a 510(k) application to FDA to add a new indication for use. Six- and 12-month data will also be collected for publication purposes.

## 2 Protocol

### 2.1 Study design

The study is a prospective, multicenter, 2-phase, controlled study. Phase 1 will include 10 subjects treated with balloon dilation.

Phase 2 will include 40 subjects randomized 1:1 to balloon dilation or control (6 weeks of continued current medical therapy). Phase 2 is designed to test the primary efficacy endpoint hypothesis that ETD symptom improvement (overall ETDQ-7 score) after balloon dilation is superior to the control group. For subjects randomized to the control arm, if ETD symptoms persist at 6 weeks after randomization (overall ETDQ-7 score  $\geq 3.0$  or change  $< 0.4$ ), the subjects will be allowed to crossover to the balloon dilation arm. Control subjects who do not have persistent ETD symptoms at 6 weeks after randomization will be exited from the study. **Figure 1** presents the study design and subject flow for Phase 2.

[figure not shown]

Figure 1. Phase 2 Study Design and Subject Flow

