## 2.3 Study endpoints

### 2.3.1 Primary endpoints

The following measures will be collected as the primary endpoints:

- Comparison of mean change in overall ETDQ-7 score from baseline to 6 weeks between balloon dilation arm and control arm
- Complication rate

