## 2.6 Sample size estimation

The sample size was calculated using PASS, Inequality Tests for Two Means (2-sample t-test) to test for superiority of improvement of ETDQ-7 scores at 6 weeks and was based on the following assumptions:

- Significance level (1-sided alpha) = 0.025
- Power = 80%
- Mean change in overall ETDQ-7 score in the balloon dilation group = -2.15
- Mean change in overall ETDQ-7 score in control group = -0.85
- Common standard deviation for both groups = 1.3

Under the assumptions outlined above, a total sample size of 34 randomized subjects (17 per arm) is adequate to test this hypothesis. To account for up to 10% attrition, a minimum of 40 subjects will be enrolled in Phase 2 of the study.

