### 2.9.5 Control arm assignment

Subjects randomized to the control arm will continue their current ETD medical treatment regimen for 6 weeks after randomization. A treatment regimen consisting of no medication is permitted if consistent with the subject's current treatment plan. Medications will be documented on the Medications CRF. Control subjects are not allowed to undergo any surgical treatments during this study period.

After the 6-week period of continued medical therapy, control subjects who continue to have ETD symptoms (defined as an overall ETDQ-7 score  $\geq 3.0$  or a change of  $< 0.4$ ) will be allowed to crossover to balloon dilation treatment and will undergo the dilation procedure and postprocedure follow-up visit schedule for the balloon dilation arm. Control subjects who do not

crossover will be exited from the study at this time. The 6-week crossover evaluation will serve as the preprocedure assessment for crossover subjects.

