#### 2.10.1 Primary and secondary endpoint assessments

##### *Mean change in overall ETDQ-7 score*

The Eustachian Tube Dysfunction Questionnaire (ETDQ-7) is a standardized, 7-item questionnaire designed to assess quality of life associated with Eustachian tube dysfunction. The 7 dimensions of the questionnaire are pressure, pain, feeling clogged, cold/sinusitis problems, crackling/popping, ringing, and feeling muffled. Each item is assessed on a 1 (no problem) to 7 (severe problem) scale and an overall score, which is the mean of the 7 dimension scores, is calculated. The questionnaire is designed to be self-completed by the subject. ETDQ-7 questionnaires will be completed at baseline and at all study visits. Changes in overall ETDQ-7 scores will be based on the mean change between the baseline assessment (or 6-week crossover

evaluation for crossover subjects) and each follow-up assessment. Standard treatment effect size may also be calculated for the mean overall ETDQ-7 score. The ETDQ-7 CRF may be considered a source document if completed directly by the subject on the CRF.

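### The control arm's self-completed 6-week ETDQ-7 is both the primary outcome and the gate to crossover dilation, so the comparison is liable to lean toward the device

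*Combined protocol and SAP*

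**What the plan says.** Section 2.3.1 sets the primary efficacy endpoint: "Comparison of mean change in overall ETDQ-7 score from baseline to 6 weeks between balloon dilation arm and control arm". Section 2.10.1 describes the ETDQ-7 as the mean of seven items, each scored 1 to 7, and adds: "The questionnaire is designed to be self-completed by the subject".

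One arm has a transnasal procedure. For the other, section 2.9.5 says: "Subjects randomized to the control arm will continue their current ETD medical treatment regimen for 6 weeks after randomization". That regimen may be no medication. No sham, masking of subjects or masked assessment is described.

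The Investigational Plan Summary describes the control arm as medical management "with ability to crossover to dilation after 6 weeks, if not improved". Sections 2.1, 2.9.5 and 2.9.7 make this numerical. Section 2.9.5 refers to "control subjects who continue to have ETD symptoms (defined as an overall ETDQ-7 score" of at least 3.0, or a change below 0.4. For such controls, section 2.1 says "the subjects will be allowed to crossover to the balloon dilation arm". For the rest it says "Control subjects who do not have persistent ETD symptoms at 6 weeks after randomization will be exited from the study". I read the change below 0.4 as an improvement of less than 0.4 points, which fits the Summary.

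The 6-week crossover evaluation supplies both the control arm's outcome and the crossover decision. Sections 2.9.5 and 2.9.7 do not say that the form must be completed before crossover is raised. Sections 2.7 to 2.7.2 plan no analysis of possible over-reporting. The analyses for missing data would not cover it, because these scores would be present but shifted.

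**The concern.** A control subject who reports a high 6-week score keeps the option of dilation. One who reports a score that is both low enough and sufficiently improved leaves the study without it. Entrants have had at least 12 months of ETD and have failed medical management (section 2.8.1), so wanting the device is plausible. Dilation subjects face no comparable gate.

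The direction is clear. Section 2.5 defines d as dilation minus control and tests for d below 0. A higher control score at 6 weeks means less control improvement, which makes d more negative. The planned t-test cannot tell such a shift from a treatment effect, and this small comparison is to support a 510(k) application (sections 1.2 and 2.4).

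**Working it through.** **Inputs from section 2.6.** "Significance level (1-sided alpha) = 0.025"; power 80%; mean changes -2.15 and -0.85, a difference of 1.30; common SD 1.3; 17 per arm needed and at least 40 enrolled, so 20 per arm without attrition.

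**The plan's own figure.** With a two-sample t-test and the noncentral t distribution, power is 0.781 at 16 per arm and 0.807 at 17 per arm. The stated 17 per arm (34 in total) reproduces.

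**Smallest significant observed difference.** Formula: t(0.975, 2n - 2) × SD × √(2/n), with an observed SD of 1.3.
- 17 per arm: standard error 1.3 × √(2/17) = 0.446; 2.037 × 0.446 = 0.91.
- 20 per arm: standard error 1.3 × √(2/20) = 0.411; 2.024 × 0.411 = 0.83.

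If the observed difference is 1.30, the uniform control-arm shift that removes significance is 1.30 - 0.91 = 0.39 at 17 per arm, or 1.30 - 0.83 = 0.47 at 20 per arm.

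**False-positive rate under an assumed shift.** Suppose dilation has no true effect and the control mean is reported b points too high. The rejection probability is the upper tail of a noncentral t with 2n - 2 degrees of freedom and noncentrality b / standard error. The values of b are assumptions, because the documents give none.

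| Assumed b | 17 per arm | 20 per arm |
|---|---|---|
| 0 | 2.5% | 2.5% |
| 0.1 | 4.1% | 4.2% |
| 0.2 | 6.4% | 6.9% |
| 0.3 | 9.6% | 10.6% |
| 0.5 | 19.2% | 21.9% |

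**What shift could the gate itself produce?** The documents give no baseline mean, so I assumed means of about 3.7 to 5.0 among subjects meeting the 3.0 entry floor. I used the plan's control change (mean -0.85, SD 1.3) and kept scores within 1 to 7. About 49% to 80% of controls then qualify without any over-reporting. Suppose some non-qualifiers raise their score to exactly 3.0.
- If all do, the control mean shifts by about 0.56 at the lowest baseline and 0.17 at the highest.
- If a quarter do, the shift is 0.25 × 0.56 = 0.14 down to 0.25 × 0.17 = 0.04.

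Put through the same noncentral t, shifts of 0.04 and 0.14 give a 1-sided error of 3.1% and 4.9% at 17 per arm, and 3.1% and 5.2% at 20 per arm. A shift of 0.5 needs nearly every non-qualifier to inflate, and only at the lowest assumed baseline.

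**The case against.** Several stronger readings are tempting, and the documents do not support them.

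- **That the comparison is biased.** The text shows an incentive. It does not show that subjects respond to it, or that they are told the 3.0 and 0.4 limits.
- **That any improvement costs a control the device.** The two conditions are joined by *or*. A control who falls from 5.5 to 3.2 has improved by 2.3 points and still qualifies. Only those both below 3.0 and improved by at least 0.4 are exited. They are the less symptomatic controls, and to gain access they would have to want a procedure whose listed risks include permanent hearing loss and carotid artery damage (section 3.2).
- **That crossover contaminates the primary comparison.** It follows the 6-week score. The problem is the incentive at the moment of scoring.
- **That the gate could create the whole planned difference.** Even the extreme illustrated shift, 0.56, is well short of 1.30.

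Two further objections carry weight. A tipping-point analysis with a uniform shift adds nothing beyond the confidence interval, because the tipping value is the 95% limit nearest zero. An instruction on visit order also has limited force, since subjects are likely to know from the outset that crossover is possible.

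What remains is a one-sided incentive that the plan neither limits nor examines. Subjects who know only that lack of improvement opens the way to dilation might inflate more broadly than the gate model assumes; the documents cannot settle this. Tympanometry, otoscopy and the Valsalva evaluation are done at the 6-week visit in both arms, but none is a primary or secondary endpoint, so they are not a planned check on the self-report.

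**Conclusion.** The concern holds as a risk. Using one unmasked, self-completed score as both outcome and gate makes the design liable to favour dilation, through an incentive confined to the control arm. The size cannot be derived from the documents. Under limited gaming of the gate the 1-sided error would be about 3% to 5% against a nominal 2.5%. An assumed shift of 0.5 gives 19.2% at the powered 17 per arm, but that is near the worst case for gaming the gate.

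These figures rest on the plan's SD of 1.3, no true effect and assumed shifts; the gate model also rests on assumed baselines. The point is minor, and worth acting on because the remedy is nearly free.

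**What to change.** 1. In sections 2.9.5 and 2.9.7, require that the subject complete the 6-week ETDQ-7, and that it be collected, before any other assessment or any discussion of crossover eligibility at that visit. Site staff should not mention the numeric threshold to the subject before then.
2. In section 2.7, make the 95% CI for the primary between-arm difference mandatory; at present confidence intervals are optional. Report its limit nearest zero as the smallest uniform control-arm shift that would remove significance.

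The crossover criterion and the sample size stay unchanged. The cost is a little site training and one line in the analysis section. The change reduces the incentive but does not remove it.

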## 2.2 Study objective

The primary objective of the study is to demonstrate the safety and efficacy of the XprESS device for treating patients with Eustachian tube dysfunction (ETD).

## 2.3 Study endpoints

### 2.3.1 Primary endpoints

The following measures will be collected as the primary endpoints:

- Comparison of mean change in overall ETDQ-7 score from baseline to 6 weeks between balloon dilation arm and control arm
- Complication rate

### 2.3.2 Secondary endpoints

The following measures will be collected as secondary endpoints:

- Mean change in overall ETDQ-7 score from baseline to follow-up (balloon dilation subjects)
- Technical success rate
- Revision dilation rate

## 2.4 Study size and duration

Initially, up to 10 subjects will be enrolled at up to 3 US investigational centers and treated with balloon dilation (phase 1). The second phase will include enrollment of an additional 40 subjects randomized 1:1 to balloon dilation or continued current medical therapy (control) at up to 7 investigational centers. Additional subjects may be added as needed upon approval from FDA.

It is anticipated that the first 10 subjects from phase 1 will be pooled with the remaining balloon dilation subjects for the final analysis cohort based on similar inclusion/exclusion criteria and data collection.

The expected duration of the study is 17 to 24 months. It is estimated that enrollment will take from 6 to 12 months. When a minimum of 34 phase 2 subjects have completed 6 weeks of follow-up, and a minimum of 25 phase 1 and phase 2 subjects treated with balloon dilation have completed at least 6 months of follow-up, a 510(k) application will be submitted to the FDA to obtain clearance for the new indication. All treated subjects will continue follow-up through 12 months for publication purposes. Control subjects who do not crossover to the balloon dilation treatment will be exited from the study at 6 weeks after randomization.

## 2.5 Study hypothesis

The study is designed to test the primary efficacy endpoint hypothesis that ETD symptom improvement after balloon dilation is superior to the control group.

The following hypothesis will be tested in the comparison of mean change from baseline in overall ETDQ-7 scores at 6 weeks using a 1-sided Student's t-test where a p value less than 0.025 will be considered statistically significant:

Ho:  $d \geq 0$

Ha:  $d < 0$

Where  $d$  is the difference between balloon dilation and control group (balloon dilation – control) for the mean change from baseline to 6 weeks in the overall ETDQ-7 score.

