### 2.7.1 Poolability analysis

Poolability of the primary efficacy endpoint between investigational centers will be evaluated. This assessment will evaluate the significance of any differences or imbalances that exist across investigational centers in the primary endpoint. Centers with less than 5 patients enrolled will be combined into a pseudocenter for purposes of analysis. To protect against having an overly large pseudocenter, when one pseudocenter exceeds 5 subjects, a second pseudocenter will be formed. This process will continue as needed each time a pseudocenter exceeds 5 subjects.

The type III p value from an ANOVA model will be used to assess center poolability for the primary efficacy endpoint. An alpha level of 0.15 will be used to assess statistical significance of the center effect.

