### 2.9.2 Baseline visit

All candidates for the study will have the following baseline clinical evaluations done **before enrollment and randomization**:

- Informed consent signed
- Baseline medical history, demographics, symptoms, and medication history in the 12-month period before enrollment
- Eligibility assessment: subjects meet all inclusion and no exclusion criteria.
- Nasal endoscopy
- Otoscopy examination
- Tympanometry
- Valsalva evaluation

- Assessment of ear infections over the 12-month period before enrollment
- Audiologic examination including a pure tone auditory (PTA) test
- EQ-5D and ETDQ-7 QOL questionnaires (completed by the study subject)
- Pregnancy test for female subjects of childbearing potential

The results of all baseline evaluations will be documented on the appropriate Case Report Forms (CRFs).

For subjects undergoing balloon dilation, preprocedure antibiotics and steroids may be prescribed at the discretion of the study physician. Medications may be prescribed to treat active infections and procedures may be rescheduled until active infections resolve.

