### 2.9.4 Randomization

Randomization assignments will be generated by an independent statistician using a distribution in variable blocks sizes for each center with a 1:1 allocation to control or balloon dilation. The master randomization list will be stored by the Sponsor. Randomization assignments will be placed into sequentially numbered and sealed envelopes. The trained study center personnel will contact Sponsor to receive the randomization assignment after the following steps have been completed:

1. All baseline evaluations have been performed
2. Subject has been determined eligible for the study (ie, inclusion/exclusion criteria reviewed)
3. Subject has signed an Informed Consent

The Sponsor will retrieve the first (or next) sequentially numbered envelope for that center and open it. The randomization assignment, including the randomization ID number and treatment assignment, will be recorded on the Randomization Enrollment Case Report Form. The Sponsor personnel will record the subject ID in the randomization log.

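### The primary t-test is sound but does not use baseline ETDQ-7 as a covariate, and poolability of the arm difference is judged by the center main effect rather than the arm-by-center term (minor)

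*Combined protocol and SAP*

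**What the plan says.** **Primary test.** Section 2.3.1 gives the primary efficacy endpoint as "Comparison of mean change in overall ETDQ-7 score from baseline to 6 weeks between balloon dilation arm and control arm". Section 2.5 tests it by "comparison of mean change from baseline in overall ETDQ-7 scores at 6 weeks using a 1-sided Student's t-test", significant below 0.025. Section 2.7 repeats the alpha level, and no section names a covariate. Section 2.10.1 records that "ETDQ-7 questionnaires will be completed at baseline and at all study visits", and section 2.9.2 places the baseline assessments before randomization.

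**Center.** Section 2.9.4 has assignments generated "using a distribution in variable blocks sizes for each center with a 1:1 allocation to control or balloon dilation". Center is absent from the primary test and appears in the analysis only in section 2.7.1: "The type III p value from an ANOVA model will be used to assess center poolability for the primary efficacy endpoint", followed by "An alpha level of 0.15 will be used to assess statistical significance of the center effect". The same section says that "Centers with less than 5 patients enrolled will be combined into a pseudocenter for purposes of analysis". It does not list the model terms, mention an arm-by-center term, or say what follows a p value below 0.15.

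**The concern.** Two separate matters are at stake.

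- **Precision.** The change score subtracts baseline with a fixed coefficient of 1. If baseline still predicts change after that, a trial of 34 to 40 subjects gives up power that an already collected variable could supply.
- **Poolability.** The endpoint is a difference between arms, so that difference is what must be similar across centers. A center main effect, with arms balanced 1:1 in each center, mainly asks whether average change differs between centers. Such a check can raise an alarm about a consistent device effect and stay silent about an inconsistent one.

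**Working it through.** **1. The plan's figure.** Inputs from section 2.6: mean changes -2.15 and -0.85, so the difference is 1.30; SD 1.3; 1-sided alpha 0.025; 17 per arm. The noncentrality is 1.30 / (1.3 × √(2/17)) = 2.915 on 32 df. Power is 80.7% (16 per arm gives 78.1%). With 10% attrition, 40 × 0.9 = 36, or 18 per arm, which gives 83.0%. The sample size reproduces.

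**2. Baseline as covariate.** Let R² be the share of the within-arm variance of change that baseline explains. For ANCOVA on arm and baseline with N = 34, the noncentrality is about 2.915 × √(30/31) / √(1 − R²) on 31 df. The factor √(30/31) is the price of estimating the slope.

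| R² | t-test | ANCOVA (arm, baseline) |
|---|---|---|
| 0 | 80.7% | 79.3% |
| 3% | 80.7% | 80.5% |
| 5% | 80.7% | 81.3% |
| 10% | 80.7% | 83.4% |
| 25% | 80.7% | 89.4% |

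Simulation agrees: 79.5 against 78.3% when baseline explains nothing, and 80.7 against 89.3% at 25%. Break-even follows from (1 − R²) × 31/30 = 1, so R² = 1/31 = 3.2%, plus a little for the lost degree of freedom: roughly 3 to 5%.

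**3. Where R² might lie.** The documents do not give it. With k = baseline SD / 6-week SD and r = their correlation, R² = (r − k)² / (1 + k² − 2rk), and the baseline SD is 1.3k / √(1 + k² − 2rk). Both k and r are assumptions.

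| k | r = 0.3 | r = 0.5 | r = 0.7 |
|---|---|---|---|
| 0.5 | 4.2% (SD 0.67) | 0% (0.75) | 7.3% (0.88) |
| 0.75 | 18.2% (0.92) | 7.7% (1.08) | 0.5% (1.36) |
| 1.0 | 35.0% (1.10) | 25.0% (1.30) | 15.0% (1.68) |

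Entry requires a score of at least 3.0 (section 2.8.1) on a 1 to 7 scale (section 2.10.1). A uniform baseline on 3.0 to 7.0 has SD 4/√12 = 1.15. Three cells exceed that and are unlikely. Of the other six, four lie above break-even, one at it, and one below.

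**4. Center.** Blocking within center removes most between-center variance from the arm difference but leaves it in the t-test's SD. Simulated with 34 subjects, 7 near-equal centers, and assumed blocks of 2 and 4:

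- Center share of variance 0.1 / 0.2 / 0.3 (assumed): t-test one-sided type I error 2.1 / 1.8 / 1.4%; t-test power 81.7 / 83.1 / 84.6%; power with center in the model 82.9 / 87.0 / 90.7%.
- Nothing explained: t-test 80.7%; arm + baseline + center 76.9%, a loss of 3.8 points.

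**5. Poolability.** With balanced arms, the mean change in center j is (control level)ⱼ + (device effect)ⱼ / 2. The center test compares that sum; the interaction test compares the device effects alone. Flagging rates at 0.15, SD 1.3, 40 evaluable:

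| Pattern | Center test (center + arm model) | Arm-by-center test |
|---|---|---|
| 6 centers, levels ±0.8, identical effect | 93% | 15% |
| 6 centers, effect ±1.0, center means cancel | 10% | 57% |
| 6 centers, effect ±1.6, center means cancel | 5% | 92% |
| 6 centers, effect ±1.6, equal control means | 80% | 92% |
| 7 centers, identical effect, center share 0.05 / 0.1 / 0.2 | 28 / 41 / 65% | 15% |
| 7 centers, random effect SD 0.4 / 0.8 / 1.2 | 20 / 33 / 48% | 21 / 37 / 58% |

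If the unlisted model does contain the interaction, the type III center test flags 92% in the first row, 15% in the third and 92% in the fourth. The missing list of terms therefore changes the answer.

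**The case against.** **The plan contains no error in the primary test.** Sections 2.5, 2.6 and 2.7 agree with each other, the test is valid, and power meets the target. This stands: adjustment is an improvement, not a correction.

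**The gain is not assured.** The largest gain in the grid (35%) needs a baseline spread almost as wide as a uniform one, and the 25% cell needs a wider one. This also stands. It is a reason to quote a range and to note that the downside is only about 1 point.

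**Center does not belong in the primary model.** Up to 7 centers cost about 4 points at 34 evaluable if nothing is explained, and they help only if centers differ. This stands, so center is proposed for a sensitivity analysis only.

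**The poolability check has no consequence, and the alternative is weak.** Nothing in section 2.5 makes the primary test conditional on section 2.7.1. The striking contrasts come from constructed patterns. Under random variation in the effect, the interaction test detects little more: with 34 of 40 evaluable and unequal centers, 19 / 32 / 47% against 18 / 30 / 43% at effect SD 0.4 / 0.8 / 1.2. In that setting 69% of simulated trials still have a center-arm cell with fewer than 2 subjects after merging, and 16% have an empty cell. All of this stands and limits the point. The main advantage of the interaction test is that it does not flag mere level differences, where the center test in the same setting flags 25 / 36 / 54% at shares 0.05 / 0.1 / 0.2.

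**Conclusion.** The point holds and is minor. The primary analysis leaves out a covariate that costs about 1 point of power at worst and could return several. The poolability criterion is aimed at average change, not at the arm difference it is meant to protect.

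Three stronger readings are tempting and are not supported:

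- *That the t-test is invalid, or the trial underpowered, because it ignores the stratum.* Leaving center out makes the test conservative (about 1.8% instead of 2.5% at an assumed 20% center share), and its power does not fall below plan. The shortfall is only against an adjusted analysis.
- *That adjustment would certainly raise power.* The documents give neither the correlation nor the SD ratio on which this depends.
- *That a poolability p value below 0.15 could overturn or block the primary result.* The documents attach no consequence to it.

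The power figures rest on the section 2.6 difference and SD. Block sizes, center shares, effect variation, k and r are assumptions. The statement that the test is valid concerns the test itself. It does not cover the exclusion in section 2.7 of subjects who drop out before receiving their assigned treatment, or the pooling of phase 1 subjects in section 2.4.

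**What to change.** **Sections 2.5 and 2.7.** Prespecify the primary analysis as ANCOVA of 6-week ETDQ-7 change on arm and baseline ETDQ-7, testing arm at 1-sided 0.025. Report the t-test as supportive. Add a sensitivity analysis that also includes center, merged as in section 2.7.1, with the grouping fixed before outcomes are analyzed.

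**Section 2.7.1.**

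- List the model terms: arm, merged center and arm-by-center. Judge consistency by the arm-by-center term at 0.15.
- Before that test, merge further any group that lacks subjects in one arm.
- Show arm differences with 95% CI by merged center whatever the p value. These will be wide: with 3 per arm, pooled SD 1.3 and 25 df, the half-width is 2.06 × 1.3 × √(2/3) ≈ 2.2.
- State that the primary result stands whatever the p value, and that a non-significant interaction does not show consistency, because power is only about 20% at an effect SD of 0.4.

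**Cost.** Wording only. All variables are already collected and the target of 40 is unchanged. The power cost is about 1 point at 34 evaluable if baseline explains nothing.
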